8.4.3 Vital signs (pulse)

Pulse (beats/minutes) will be recorded in a sitting position after resting for five minutes at the specified visits (Section [2](#)).

8.4.4 Electrocardiogram

An electrocardiogram (ECG) will be performed at the visits specified in the flow chart (Section [2](#)). The investigator or delegate must sign, date and interpret the ECG by using the following categories:

- Normal
- Abnormal: Was the result clinically significant? (Yes/No)

Clinically significant is an abnormality that suggests a disease and/or organ toxicity and is of a severity that requires active management. Active management includes active treatment or further investigations, for example, change of medicine dose or more frequent follow-up due to the abnormality.

If the result is clinically significant, the investigator must report such an abnormal finding as an AE or SAE (see Section [12.2](#)).

ECG performed at screening will be considered as baseline.

8.4.5 Hypoglycaemic episodes

Liraglutide increases insulin secretion and reduces glucagon secretion in a glucose dependent manner. Thus, the stimulation of insulin release and inhibition of glucagon release subsides as the blood glucose decreases and approach euglycemia. Therefore, the risk of hypoglycaemia in subjects without T2DM is considered to be low.

A hypoglycaemic episode during the trial should be recorded as an AE according to standard AE reporting (see Section [12](#)).

Subjects should be instructed in potential symptoms of hypoglycaemia: sweating, trembling, hunger or palpitations (rapid or irregular heart beat), confusion, drowsiness, speech difficulty, visual disturbances, odd behaviour, impaired balance or incoordination (reduced ability to coordinate movement).

According to ADA classification, a severe episode of hypoglycaemia is defined as an episode requiring assistance of another person to actively administer carbohydrate, glucagon, or take other corrective actions. Plasma glucose concentrations may not be available during an event, but neurological recovery following the return of plasma glucose to normal is considered sufficient evidence that the event was induced by low plasma glucose concentration⁵¹. Such a severe episode of hypoglycaemia must be reported as a SAE (see Section [12.2](#)).

Blood glucose meters will not be handed out to subjects in this trial.

8.4.6 Patient Health Questionnaire-9

The patient health questionnaire-9 (PHQ-9) is a 9-item depression module of the patient health questionnaire, which is a self-administered diagnostic tool used for assessment of mental disorders⁵². The questionnaire will be available in a linguistically validated version in subject's fluent language. Subjects should be given the opportunity to complete the questionnaires by themselves without interruption. It takes approximately 10 minutes to complete.

A PHQ-9 \geq 15 excludes the subject from participation in the trial.

8.4.7 Columbia Suicidal Severity Rating Scale

The Columbia suicidal severity rating scale (C-SSRS)⁵³ is a detailed questionnaire assessing both suicidal behaviour and suicidal ideation. The questionnaire will be administered as an interview by the investigator or a qualified delegate. The questionnaire will be available in a linguistically validated version in the subject's fluent language. It takes approximately 10 minutes to complete.

Prior to administering the C-SSRS questionnaire, the investigator or qualified delegate must complete sufficient training. Any suicidal ideation of type 4 or 5 within the past 30 days at screening or randomisation excludes the subject from participation in the trial.

8.4.8 Breast and colon neoplasms follow up

These forms must be completed at the end-of-treatment and follow-up visit, even if a subject prematurely discontinues treatment with trial product. The breast neoplasm follow up form should be filled in only for female subjects.

If a subject withdraws consent, the subject must be encouraged to provide this information.

8.5 Laboratory assessments

The laboratory analyses will be performed by a central laboratory. The central laboratory may utilise subcontractors.

Descriptions of assay methods, laboratory supplies and procedures for obtaining samples, handling, transportation and storage of samples and information regarding who will perform the assessments, will be described in a trial specific laboratory manual, provided by the central laboratory (for central laboratory details, see [Attachment 1](#)).

The laboratory equipment may provide analyses not requested in the protocol but produced automatically in connection with the requested analyses according to specifications in the laboratory standard operating procedures. Such data will not be transferred to the trial database, but abnormal values will be reported to the investigator. The investigator must review all laboratory results for concomitant illnesses and AEs and report these according to Section [8.2.2](#) and Section [12](#).

Laboratory samples may be drawn on another day than the day of the actual visit, as long as it is within the visit window outlined in the flow chart (see Section [2](#)). For some of the samples drawn during the trial, it is required that the subject is fasting. If a subject is not fasting at these visits, the fasting blood sampling must, as a minimum, be re-scheduled within the visit window.

Laboratory results will be sent by the central laboratory to the investigator on an on-going basis.

Samples will be destroyed no later than at finalisation of the clinical trial report (CTR).

The laboratory provides results to the trial sites in the units preferred by the trial sites while the results that are transferred to the trial database will always be in SI units.

Only laboratory samples specified in the protocol must be sent to the central laboratory for analysis; if additional laboratory sampling is needed (e.g., to follow up on AEs) this must be done at a local laboratory.

For laboratory report values outside the reference range, the investigator must specify whether the value is clinically significant or not. If clinically significant, the investigator must report these as clinical laboratory adverse events (CLAE) according to Section [12.1.1](#).

All laboratory report printouts must be reviewed, signed and dated by the investigator or delegate. The evaluation of screening results must be dated and signed prior to visit 2 (randomisation), for the subsequent visits preferably on the day of evaluation.

8.5.1 Laboratory assessments for efficacy

Blood samples must be collected at the specified visits (Section [2](#)).

- HbA_{1c}
- Fasting plasma glucose (FPG)
- Lipids (TC, LDL cholesterol, HDL cholesterol, VLDL cholesterol, TG, FFA)

A FPG result ≤ 3.9 mmol/L (70 mg/dL) should not be reported as a hypoglycaemic episode but as a CLAE at the discretion of the investigator (see Section [12.1.1](#)).

8.5.2 Laboratory assessments for safety

Pregnancy test

Females of childbearing potential will have a human chorionic gonadotropin (hCG) serum pregnancy test performed at the visits specified in the flow chart (see Section [2](#)).

Urine pregnancy tests will be performed for females of childbearing potential if there is suspicion of pregnancy or if she misses a menstrual period, at the visits specified in the flow chart (Section [2](#)). She should contact the site to come in for a urine pregnancy test. Urine pregnancy kits will be supplied by the central laboratory.

Pregnancy testing will not be required for women not of childbearing potential (see Section [8.2.4](#))

Biochemistry

Blood samples for biochemistry must be collected at the specified visits (Section [2](#)).

- Creatinine
- Urea (blood urea nitrogen)
- Uric acid
- Alanine aminotransaminase (ALT)
- Aspartate aminotransferase (AST)
- Alkaline phosphatase (ALP)
- Albumin
- Amylase
- Lipase
- Sodium
- Potassium
- Calcium, total
- Calcitonin (please refer to [Appendix A](#) for actions to be taken if calcitonin is ≥ 10 ng/L)
- TSH*
- Bilirubin, total (TBL)
- hs-CRP**
- GFR, estimated

*If TSH levels are out of normal range, the investigator must perform additional testing:

- Total and free T3 and T4 and Free Thyroid Index
- Thyroid peroxidase antibodies

** hs-CRP is only measured at Visit 2 and Visit 24.

Haematology

Blood samples for haematology must be collected at the specified visits (Section [2](#)).

- Haemoglobin
- Haematocrit
- Thrombocytes
- Erythrocytes
- Leucocytes

8.6 Other assessments

8.6.1 Trial product usage

Information on premature discontinuation, and permanent discontinuation of trial product will be collected and recorded in the eCRF. If the trial product is re-started, the investigator must note this in the medical record.

8.6.2 Food diary and tracking of physical activity

The subjects will be requested to fill in a food diary daily, where all meals and their caloric content are recorded. The interventionist can provide a paper food diary or the subject can use another tracker, tool or app to register food intake, as preferred by the subject.

Daily minutes of physical activity will be captured using a device provided by Novo Nordisk. The subject's adherence with diet and physical activity must be reviewed at all CMS-IBT visits by the interventionist (see Section [8.7.1](#)). The adherence will be further recorded in the eCRF.

8.6.3 Training in the PDS290 pen-injector

The subjects must be trained in how to handle the PDS290 pen-injector when handed out the first time. Training must be repeated during the trial at each visit if needed, in order to ensure correct use of the device. The following should be emphasised:

- Always use a new needle for each injection as this will prevent contamination and blocked needles
- When using the first time, priming the pen to ensure product flow
- The needle should be kept in the skin while counting slowly to 6 (or as described in the direction for use) after the dose counter has returned to zero after injection. If the needle is removed too early then the full dose may not have been delivered.

8.6.4 Inquire about mood

The subject should be asked about the mood as per flow chart (see Section [2](#)), for example – ‘How has your mood been since the last contact?’

In case the subject reports any adverse events, these should be collected and reported as an AE. Depression and suicidal ideation/behaviour should be reported as AEs requiring additional data collection (see Section [8.4.2.2](#) and Section [12](#)).

8.7 Subject compliance

Throughout the trial, the investigator will remind the subjects to follow the trial procedures and requirements to ensure subject compliance. If a subject is found to be non-compliant, the investigator will remind the subject of the importance of following the instructions given including taking the trial products as prescribed.

Compliance with trial product: At each visit, the investigator should ask the subject whether the subject has continuously been using the trial product since last visit. If the subject has stopped using

trial product, the investigator should fill in the date for the last dose in the eCRF. If the subject has had a pause using trial product longer than one week since last visit, but has started using trial product again, the investigator should fill in the dates corresponding to the last day on trial product and the first day on trial product in the eCRF.

8.7.1 Adherence to dietary and physical activity

Adherence to the dietary and physical activity will be assessed by the interventionist performing the CMS-IBT at all visits. At each CMS-IBT session, the interventionist must, for each calendar week since the last visit, assess and record the number of days per calendar week, where the subject has entered information in the food diary (see Section [5.3.2](#)). In addition, how physically active the subject has been per week for each calendar week since the last visit will be recorded. The result must be noted in the subjects' record in eCRF.

If a subject is found to be non-adherent, the interventionist should remind the subject of the importance of following the advice given. The interventionist will help the subjects solve issues with non-adherence as part of the counselling (see Section [5.3.2](#)).

8.8 Additional safety assessments

8.8.1 Suspicion of acute pancreatitis

If pancreatitis is suspected, trial product should promptly be discontinued (no 'treatment status' session should be made in IWRS before diagnosis of acute pancreatitis is confirmed) and appropriate management should be initiated. Appropriate additional examinations must be performed, including local measurement of amylase and lipase.

The event should be reported as an AE requiring additional data collection (see Section [8.4.2.2](#) and Section [12](#)).

The diagnosis of acute pancreatitis requires two of the following three features:

- Abdominal pain consistent with acute pancreatitis (acute onset of a persistent, severe, epigastric pain often radiating to the back)
- Serum lipase activity (and/or amylase activity) at least three times greater than the upper limit of normal
- Characteristic findings of acute pancreatitis on imaging (CT/MRI).

Abdominal pain

Most patients with acute pancreatitis experience abdominal pain that is located generally in the epigastrium and radiates to the back. The onset of the pain may be swift reaching maximum intensity within 30 minutes; it is frequently unbearable and characteristically persists for more than

24 hours without relief. The pain is often associated with nausea and vomiting. Physical examination usually reveals severe upper abdominal tenderness at times associated with guarding.

Lipase and amylase

In general, both amylase and lipase are elevated during the course of acute pancreatitis. The serum lipase may remain elevated slightly longer than amylase. The level of the serum amylase and/or lipase does not correlate with the severity of acute pancreatitis. In general, serum lipase is thought to be more sensitive and specific than serum amylase in the diagnosis of acute pancreatitis.

If acute pancreatitis is confirmed, the subject must be permanently discontinued from trial product and appropriate treatment and careful monitoring of the subject should be initiated. Furthermore, the subject should still remain in the trial (see Section [8.1](#)).

If acute pancreatitis is ruled out, trial product should be re-initiated at the investigator's discretion.

8.8.2 Suspicion of acute gallstone disease

In case of suspicion of acute gallstone disease or cholelithiasis, the trial product should promptly be discontinued (no 'treatment status' session should be made in IWRS before a diagnosis of acute gallstone disease is confirmed). Appropriate treatment and careful monitoring should be initiated. Furthermore, the subject should remain in the trial (see Section [8.1](#)).

The event should be reported as an AE requiring additional data collection (see Section [8.4.2.2](#) and Section [12](#)).

If acute gallstone disease is confirmed, the trial product must be permanently discontinued. Appropriate treatment and careful monitoring of the subject should be initiated. Furthermore, the subject should remain in the trial (see Section [8.1](#)).

Trial product can be restarted at the investigator's discretion if cholelithiasis is ruled out or the gallbladder has been removed.

8.8.3 Neoplasm

In case of neoplasm, please consider if the trial drug should be discontinued (no 'treatment status' session should be made in IWRS before a diagnosis is confirmed). The event must be reported as an AE requiring additional data collection (see Section [8.4.2.2](#) and Section [12](#)).

Appropriate treatment and careful monitoring of the subject should be initiated as per local clinical practice. Furthermore, the subject should be encouraged to remain in the trial (see Section [8.1](#)).

Trial product can be re-initiated at the investigator's discretion if diagnosis is not supported.

8.8.4 Hepatic event (suspicion of drug-induced liver injury)

Please consider discontinuing trial product if :

- 1) ALT or AST >5xUNL, or
- 2) ALT or AST > 3x UNL and (total bilirubin >2xUNL or INR >1.5), or
- 3) ALT or AST >3xUNL with the appearance of fatigue, nausea, vomiting, right upper quadrant pain or tenderness, fever, rash, and/or eosinophilia (>5%).

For the above events, prompt repeat testing at central laboratory, of ALT, AST, ALP, INR and total bilirubin should be done. Thereafter, repeat testing (at central laboratory) of ALT, AST, ALP, INR and total bilirubin should be done regularly until the abnormalities return to normal or baseline state. Additional clinical information such as related symptoms, risk factors and contributing conditions (e.g. viral hepatitis, autoimmune hepatitis, alcoholic hepatitis, hepatobiliary or pancreatic disorders) should be gathered to seek a possible cause of the observed laboratory test abnormalities. Although the trial product is discontinued, no ‘treatment status’ session should be made in IWRS and the subject should remain in the trial.

The event should be reported as an AE requiring additional data collection (see Section [8.4.2.2](#) and Section [12](#)).

If DILI is confirmed, the subject should permanently discontinue the trial product. Appropriate treatment and careful monitoring of the subject should be initiated. However, the subject should remain in the trial (see Section [8.1](#)).

Trial product can be re-initiated at the investigator’s discretion, if diagnosis of DILI is not supported.

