6.5 Criteria for premature discontinuation of trial product

Efforts must be made so that subjects attend and complete all scheduled visit procedures. Subjects should stay in the trial regardless of adherence to randomised treatment, visit schedule or missing assessments. Only subjects who decline any further contact with the site in relation to the trial or withdraw consent are considered as withdrawn from the trial (see Section [6.6](#)).

The subject may be prematurely discontinued from trial product at the discretion of the investigator due to a safety concern.

The subject must be prematurely discontinued from trial product if the following applies:

1. Included in the trial in violation of any of the inclusion and/or exclusion criteria and/or randomisation criteria
2. Safety concern (not covered by any of below criteria) or unacceptable intolerability to trial product, as judged by the investigator

3. Hypersensitivity to trial product(s). If a hypersensitivity reaction occurs, discontinue trial product and other suspect medications and promptly seek medical advice
4. Pregnancy
5. Intention of becoming pregnant
6. Suspicion of pancreatitis (see Section [8.4.2.2](#) and [8.8.1](#))
7. Suspicion of acute gallstone disease (see Section [8.4.2.2](#) and [8.8.2](#))
8. Suspicion of drug-induced liver injury (DILI) (see Section [8.4.2.2](#) and [8.8.4](#))
9. Calcitonin ≥ 100 ng/L
10. Psychiatric disorder(s) that cannot be adequately treated with psycho- and/or pharmacotherapy (see Section [8.4.2.2](#), [8.8.5](#) and [8.6.4](#)).
11. Initiation of anti-obesity medication and/or (plans for) weight loss surgery
12. Initiation of treatment with glucagon-like peptide-1 receptor agonist (GLP-1 RA)
13. Simultaneous participation in another clinical trial of an approved or non-approved investigational medicinal product

See Section [8.1](#) for procedures to be performed for subjects discontinuing trial product prematurely.

It is allowed for subjects meeting the premature discontinuation criteria or who have wished to discontinue prematurely to be restarted on the trial product should the suspicion not be confirmed or if the condition has been resolved at the investigator's discretion. Trial product may be restarted for subjects meeting discontinuation criteria 7 should the gallbladder be removed.

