If a subject meets a discontinuation criterion, the trial product must be immediately discontinued and the date should be noted in the medical records and eCRF. Discontinuation can be either temporary or permanent. The last paragraph of Section [6.5](#) outlines which discontinuation can be considered temporary. The investigator must note down the date in the medical record and the eCRF once there is resolution and the subject has re-started the trial product.

The subject may also wish to discontinue trial product temporarily or permanently, irrespective meeting any criteria. Discontinuation of treatment with trial product, whether temporary or permanent, must not prompt the investigator to withdraw the subject from the trial. Instead, the subject should maintain adherence to trial visits (including CMS-IBT) and procedures to the extent possible.

In cases where the subject is not willing to attend all scheduled visits after discontinuation of trial product, efforts must be made to collect as much of the scheduled data as possible. Especially important is collection of the data points (primarily body weight) at visit 24 (week 56). Statistical considerations emphasizing the importance can be found in Section [17](#).

Premature trial product discontinuation should be registered in the eCRF and in IWRS. The trial product can be interrupted by performing a 'treatment status' session in IWRS, to indicate subject should no longer receive trial product. The primary reason for discontinuation of trial product must be specified when recording the treatment discontinuation in the eCRF. If the discontinuation of trial product is judged permanent or of a longer period, drug accountability until discontinuation must be performed in IWRS.

If the subject has previously discontinued trial product, it is possible, at the discretion of the investigator and at the wish of the subject, to re-initiate treatment with trial product. This will only apply, if it can be confirmed that the subject has not withdrawn consent, and does not fulfil any of the criteria leading to permanent discontinuation or if a criterion leading to temporary discontinuation has been resolved. A 'treatment status' session is performed in the IWRS, to indicate that the subject should again receive trial product. See Section [10](#) for registration in IWRS. This should be further noted in the medical records and eCRF.

Withdrawal from trial

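### Suspected drug-induced liver injury: Protocol 6.5 and 8.1 make stopping trial product mandatory, but 8.8.4, which 6.5 cites, only asks sites to consider it

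*Protocol*

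**What the plan says.** Protocol 6.5 opens its mandatory list with "The subject must be prematurely discontinued from trial product if the following applies". Criterion 8 on that list is "Suspicion of drug-induced liver injury (DILI", with cross-references to 8.4.2.2 and 8.8.4. Section 8.1 adds the timing: "If a subject meets a discontinuation criterion, the trial product must be immediately discontinued".

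Section 8.8.4 carries suspicion of DILI in its heading. It begins "Please consider discontinuing trial product if" and gives three triggers: a transaminase elevation alone, a lower elevation together with raised bilirubin or INR, and a lower elevation together with symptoms or eosinophilia. It then asks for repeat testing and a search for other causes. After that it says that no IWRS treatment-status session should be made, in a sentence written as though product had already been stopped. Firm stopping language appears only once DILI is confirmed, when discontinuation is to be permanent.

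Section 8.4.2.2, the other section cited by criterion 8, says that on suspicion product should be stopped until the abnormalities have resolved.

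**The concern.** The same event draws a mandatory, immediate stop in one place and an invitation to consider stopping in another, and the first place sends the reader to the second. An investigator who reaches an 8.8.4 trigger and keeps the subject on product has followed 8.8.4 but may have breached 6.5 and 8.1. A monitor has no consistent basis for deciding whether that is a protocol deviation.

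This is a safety stopping rule. The second trigger includes the transaminase-plus-bilirubin pattern that section 12.1.2 makes a compulsory SAE when no alternative aetiology exists. Section 12.1.2 is a reporting rule and says nothing about stopping, but it shows that the *consider* wording extends to a pattern the protocol itself treats as serious.

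The analysis is touched to a lesser degree. The primary jump-to-reference rule imputes every missing week-56 weight from placebo, whether or not the subject had stopped product, so the classification itself does not matter there; stopping or continuing could still change an individual's weight. Under SAP 2.3.3 the efficacy estimand uses data only up to first discontinuation, apart from pauses of less than eight days, so a stop also changes which of that subject's data are used.

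**Working it through.** **1. The instructions side by side**

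| Protocol section | What sets it off | Strength |
|---|---|---|
| 6.5, criterion 8 | Suspicion of DILI | Must stop |
| 8.1 | Any discontinuation criterion met | Must stop, immediately |
| 8.4.2.2 | Suspicion of DILI | Should stop |
| 8.8.4, at its triggers | Headed as suspicion of DILI | Consider stopping |
| 8.8.4, later | Confirmed DILI | Should stop permanently |

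Amendment 1 lists changes to sections 1, 2, 4.2.2.1, 4.2.2.2, 8.5.2, 17.1 and 17.4.2. None of the sections in the table is among them. The SAP does not address the point.

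**2. Is an 8.8.4 trigger a suspicion of DILI?** The heading of 8.8.4 says so. The section also has the event reported as one requiring additional data collection, and the only hepatic category in 8.4.2.2 and 12.1.5 is the one labelled as suspicion of DILI. Neither section gives another definition of suspicion.

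**3. Is this the protocol's general drafting style?** Four of the 13 mandatory criteria in 6.5 cite an 8.8 section:

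- Criterion 6 (pancreatitis) cites 8.8.1, which directs prompt stopping on suspicion.
- Criterion 7 (gallstone disease) cites 8.8.2, which does the same.
- Criterion 8 (DILI) cites 8.8.4, which says consider.
- Criterion 10 cites 8.8.5, which says consider. That criterion is limited to "Psychiatric disorder(s) that cannot be adequately treated with psycho- and/or pharmacotherapy", whereas 8.8.5 applies to any depression or suicidal ideation or behaviour, so the two can coexist.

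Section 8.8.3 (neoplasm) also says consider, but no criterion in 6.5 cites it. Criterion 8 is the only mismatch on the same condition.

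**4. Related wording**

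- *Restart.* Section 8.1 says that the last paragraph of 6.5 "outlines which discontinuation can be considered temporary". That paragraph allows restart "should the suspicion not be confirmed or if the condition has been resolved". Section 8.8.4 allows it only if the diagnosis is not supported and makes confirmed DILI permanent. Section 8.1 bars re-initiation where a criterion for permanent discontinuation is fulfilled, and section 10 bars it while any discontinuation criterion is met, so the gap is partly closed.
- *IWRS.* The no-session sentence in 8.8.4 lacks the limit, found in 8.8.1 to 8.8.3 and 8.8.5, that it applies only until diagnosis. Its position just before the paragraph on confirmed DILI suggests the same scope. Section 10 registers every discontinuation, temporary or permanent, with such a session.
- *Cross-reference.* Section 8.4.2.2 sends the reader to 8.8.3 for the liver tests; they are in 8.8.4.

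**5. Possible effect on the primary endpoints (illustration).** Inputs from Protocol 17.1 are 141 subjects per arm, a completer difference of 5 points, and expected differences of 3.5 points in % weight change and 19 percentage points in 5% responders. The number affected, k, is not in the documents; k = 1 to 5, all on liraglutide and each shifting by the full 5 points, is an assumption.

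- Shift in arm mean = 5k/141. For k = 1: 5/141 = 0.035 points, and 0.0355/3.5 = 1.0% of the expected difference. For k = 5: 25/141 = 0.18 points, and 0.1773/3.5 = 5.1%.
- Shift in responder proportion if each subject also changes status = k/141. For k = 1: 0.7 percentage points. For k = 5: 3.5 percentage points, against 19.

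**The case against.** The strongest counter-reading is that criterion 8 concerns suspicion that the *drug* caused the injury, while the 8.8.4 triggers are raw laboratory and symptom thresholds. Section 8.8.4 itself asks for other causes such as viral, autoimmune or alcoholic hepatitis. On that reading a trigger prompts an assessment, and the mandatory stop applies once the investigator suspects the drug. This is coherent, and it makes the conflict conditional on whether a trigger is itself suspicion. But the protocol never says that it is not, and the heading and reporting route of 8.8.4 point the other way.

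It is also fair to note that 8.8.4 later presumes product has been stopped, and that 8.4.2.2 does direct stopping. Those sentences add to the inconsistency; they do not settle it.

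There are real backstops: the general provision "The subject may be prematurely discontinued from trial product at the discretion of the investigator due to a safety concern"; mandatory criterion 2, for an investigator-judged safety concern not covered by the later criteria; prompt repeat testing; SAE reporting; and stopping after confirmation. Section 18.1 lists no hepatic risk. These points limit the likely harm, but none says whether product must be stopped at an 8.8.4 trigger.

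The restart, IWRS and cross-reference points are minor and would not carry the finding alone. The objection that the numerical illustration rests on an arbitrary k is also fair; it serves only to show that the statistical effect is likely to be small.

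**Conclusion.** The concern holds. For one condition the current text gives a mandatory immediate stop (6.5, 8.1), a recommended stop (8.4.2.2) and a stop to be considered (8.8.4), and it does not say how they fit together. It needs correcting because it is a safety stopping rule on which sites can act in opposite ways while each follows the text.

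The conclusion depends on reading an 8.8.4 trigger as suspicion of DILI, which the text supports but does not state outright. If the sponsor intended otherwise, the protocol must say so. SAP 1.2 refers to protocol version 5 with Amendment 1, whereas the protocol available is version 4.0 with Amendment 1; nothing in the documents suggests that the relevant sections changed. The effect on the primary comparison is probably small. This review takes no view on which stopping rule is right.

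**What to change.** Reconcile section 6.5 (criterion 8 and the last paragraph), 8.1, 8.4.2.2, 8.8.4 and section 10 so that one stopping instruction, one restart condition and one IWRS rule apply to suspected DILI, and likewise to confirmed DILI. State explicitly whether reaching an 8.8.4 trigger is itself suspicion under criterion 8. Correct the cross-reference in 8.4.2.2 to point to the hepatic section. The sponsor's medical team decides which rule stands.

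The cost is a protocol clarification and a site letter, with no change to data collection, sample size or analysis. If the chosen wording changes a discontinuation rule and so needs a formal amendment, section 25 requires approval before it is implemented, except where an immediate hazard must be removed.
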